9.2 Agent Ordering and Agent Accountability

NCI-supplied agents may be requested by eligible participating Investigators (or their authorized designee) at each participating institution. The CTEP-assigned protocol number must be used for ordering all CTEP-supplied investigational agents. The eligible participating investigators at each participating institution must be registered with CTEP, DCTD through an annual submission of FDA Form 1572 (Statement of Investigator), NCI Biosketch, Agent Shipment Form, and Financial Disclosure Form (FDF). If there are several participating investigators at one institution, CTEP-supplied investigational agents for the study should be ordered under the name of one lead participating investigator at that institution.

In general, sites may order initial agent supplies when a subject is being screened for enrollment onto the study.

9.3 Clinical Drug Request

Submit agent requests through the PMB Online Agent Order Processing (OAOP) application. The current versions of the IBs for the agents will also be accessible to site investigators and research staff through the PMB Online Agent Order Processing (OAOP) application. Access to OAOP requires the establishment of a CTEP Identity and Access Management (IAM) account and the maintenance of an “active” account status, “current” password, and active person registration status. For questions about drug orders, transfers, returns, or accountability call or email PMB anytime. Refer to the PMB’s website for specific policies and guidelines related to agent management. Questions about IB access may be directed to the PMB IB coordinator via email.

9.4 Agent Inventory Records

The investigator, or a responsible party designated by the investigator, must maintain a careful record of the receipt, dispensing and final disposition of all agents received from the PMB using the appropriate NCI Investigational Agent (Drug) Accountability Record (DARF) available on the CTEP forms page. Store and maintain separate NCI Investigational Agent Accountability Records for each agent, strength, formulation and ordering investigator on this protocol.

9.5 Investigator Brochure Availability

The current versions of the IB for the agent will be accessible to site investigators and research staff through the PMB Online Agent Order Processing (OAOP) application. Access to OAOP requires the establishment of a CTEP IAM account and the maintenance of an “active” account status, a “current” password and active person registration status. Questions about IB access may be directed to the PMB IB coordinator via email.

10.0 CRITERIA FOR REMOVAL FROM PROTOCOL THERAPY AND OFF STUDY CRITERIA

10.1 Criteria for Removal from Protocol Therapy

- Clinical (including physical examination or serum tumor markers) or radiographic evidence of progressive disease (See [Section 12.0](#)).
- Adverse Events requiring removal from protocol therapy (See [Section 6.0](#)).
- Refusal of further protocol therapy by patient/parent/guardian.
- Non-compliance that in the opinion of the investigator does not allow for ongoing participation.
- Completion of planned therapy on Day 42.
- Physician determines it is not in the patient's best interest.
- Repeated eligibility laboratory studies (CBC with differential, bilirubin, ALT (SGPT) or serum creatinine) are outside the parameters required for eligibility prior to the start of AZD1775 (MK-1775) (See [Section 8.1](#)).
- Study is terminated by Sponsor.
- Pregnancy

Patients who are removed from protocol therapy during radiation therapy should continue to have the required observations in [Section 8.1](#) until the originally planned end of treatment or until all adverse events have resolved per [Section 13.4.4](#), whichever happens LATER. The only exception is with documentation of the patient's withdrawal of consent.

Patients who are off protocol therapy are to be followed as described in [Section 8.2](#) until they meet the criteria for Off Study (see below). Ongoing adverse events, or adverse events that emerge after the patient is removed from protocol therapy, but within 30 days of the last dose of investigational agent, must be followed and reported via RAVE and CTEP-AERS (if applicable). Serious adverse events that occur during the follow-up period (more than 30 days after the last administration of investigational agent) and have an attribution of possible, probable, or definite require reporting per [Footnote 1 of Table A](#). Follow-up data will be required unless consent is withdrawn.

10.2 Off Study Criteria

- Death
- Lost to follow-up
- Withdrawal of consent for any further required observations or data submission.
- Enrollment onto another COG therapeutic (anti-cancer) study

11.0 STATISTICAL AND ETHICAL CONSIDERATIONS

11.1 Sample Size and Study Duration

A minimum of 2 evaluable patients will be entered at each dose level for determination of MTD. Once the MTD or recommended phase 2 dose has been defined, up to 6 additional patients with DIPG may be enrolled to acquire PK data in a representative number of young patients (i.e. patients < 12 years old). Review of the enrollment rate into a recent COG study of DIPG, ACNS0927, indicates that 1-2 patients per month are available, which will permit completion of the study within 20-38 months if all dose levels are studied with 6 evaluable patients. A maximum of 65 patients is anticipated, which accounts for potential expansion to 12 patients at each dose level (see [Section 11.2](#)) and an inevaluable rate of 20%.

As of Amendment #4, 26 patients have enrolled onto the study. An additional 24 evaluable patients may be required to evaluate Dose Levels 5-7, which will permit completion of the study within 12-24 months if these dose levels are studied with 6 evaluable patients each and an additional 6 patients are required for PK analysis. Up to 51 additional patients may be enrolled, which accounts for potential expansion to 12 patients at each dose level (see [Section 11.2](#)) and an inevaluable rate of 20%. This would be expected to be completed within 26-51 months. The maximum accrual for the study will increase from 65 to 77 patients.

11.2 Definitions

Evaluable For Adverse Effects

Any patient who experiences DLT at any time during protocol therapy is considered evaluable for Adverse Effects. Patients without DLT who receive at least 85% of the prescribed dose of AZD1775 (MK-1775) and radiation therapy within 8 weeks of starting protocol therapy and had the appropriate toxicity monitoring studies performed are also considered evaluable for Adverse Effects. Patients who are not evaluable for Adverse Effects at a given dose level will be replaced.

Maximum Tolerated Dose

The MTD will be the maximum dose at which fewer than one-third of patients experience DLT (See [Section 5.4](#)) during therapy. In the event that two DLTs observed out of 6 evaluable patients are different classes of Adverse Effects (e.g. hepatotoxicity and myelosuppression), expansion of the cohort to 12 patients will be considered if all of the following conditions are met:

- One of the DLTs does not appear to be dose-related.
- The Adverse Effects are readily reversible.
- The study chair, DVL statistician, DVL committee chair or vice chair, and IND sponsor all agree that expansion of the cohort is acceptable.

If fewer than 1/3 of patients in the expanded cohort experience dose-limiting toxicities, the dose escalation can proceed.

11.3 Dose Escalation and Determination of MTD

The rolling six phase 1 trial design will be used for the conduct of this study.²⁹ Due to the

unknown pharmacokinetics of AZD1775 (MK-1775) after prolonged administration, the age requirement of the first patient enrolled on dose level 1 will be \geq 7 years. The study will be temporarily closed to accrual until PK analysis of this patient is completed. Pending results, the study will either open a slot to another patient 7 years of age or older, or to children greater than 3 years of age. Upon agreement from the study team, the rolling six design may then be utilized: Two to six patients can be concurrently enrolled onto a dose level, dependent upon (1) the number of patients enrolled at the current dose level, (2) the number of patients who have experienced DLT at the current dose level, and (3) the number of patients entered but with tolerability data pending at the current dose level. Accrual is suspended when a cohort of six has enrolled or when the study endpoints have been met.

Dose level assignment is based on the number of participants currently enrolled in the cohort, the number of DLTs observed, and the number of participants at risk for developing a DLT (i.e., participants enrolled but who are not yet assessable for toxicity). For example, when three participants are enrolled onto a dose cohort, if toxicity data is available for all three when the fourth participant entered and there are no DLTs, the dose is escalated and the fourth participant is enrolled to the subsequent dose level. If data is not yet available for one or more of the first three participants and no DLT has been observed, or if one DLT has been observed, the new participant is entered at the same dose level. Lastly, if two or more DLTs have been observed, the dose level is de-escalated. This process is repeated for participants five and six. In place of suspending accrual after every three participants, accrual is only suspended when a cohort of six is filled. When participants are inevaluable for toxicity, they are replaced with the next available participant if escalation or de-escalation rules have not been fulfilled at the time the next available participant is enrolled onto the study.

The following table provides the decision rules for enrolling a patient at (i) the current dose level (ii) at an escalated dose level, (iii) at a de-escalated dose level, or whether the study is suspended to accrual:

# Pts Enrolled	# Pts with DLT	# Pts without DLT	# Pts with Data Pending	Decision
2	0 or 1	0, 1 or 2	0, 1 or 2	Same dose level
2	2	0	0	De-escalate*
3	0	0, 1 or 2	1, 2 or 3	Same dose level
3	1	0, 1 or 2	0, 1 or 2	Same dose level
3	0	3	0	Escalate**
3	≥ 2	0 or 1	0 or 1	De-escalate*
4	0	0, 1, 2 or 3	1, 2, 3 or 4	Same dose level
4	1	0, 1, 2 or 3	0, 1, 2 or 3	Same dose level
4	0	4	0	Escalate**
4	≥ 2	0, 1 or 2	0, 1 or 2	De-escalate*
5	0	0, 1, 2, 3 or 4	1, 2, 3, 4 or 5	Same dose level
5	1	0, 1, 2, 3 or 4	0, 1, 2, 3 or 4	Same dose level
5	0	5	0	Escalate**
5	≥ 2	0, 1, 2 or 3	0, 1, 2 or 3	De-escalate*
6	0	0, 1, 2, 3, or 4	2, 3, 4, 5 or 6	Suspend

THIS PROTOCOL IS FOR RESEARCH PURPOSES ONLY, SEE PAGE 1 FOR USAGE POLICY

6	1	0, 1, 2, 3 or 4	0, 1, 2, 3 or 4	Suspend
6	0 or 1	5 or 6	0 or 1	Escalate**
6	≥ 2	0, 1, 2, 3 or 4	0, 1, 2, 3 or 4	De-escalate*

* If six patients already entered at next lower dose level, the MTD has been defined.

**If final dose level has been reached, the recommended dose has been reached.

If two or more of a cohort of up to six patients experience DLT at a given dose level, then the MTD has been exceeded and dose escalation will be stopped (see [Section 11.2.2](#) for exception to rule).

In addition to determination of the MTD, a descriptive summary of all toxicities will be reported.

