5.5 Definition of Dose-Limiting Toxicity (DLT)

DLT will be defined as any of the following events that are possibly, probably or definitely attributable to AZD1775 (MK-1775). The DLT observation period for the purposes of dose-escalation will be the entire duration of radiation therapy.

Dose limiting hematological and non-hematological toxicities are defined differently.

Interruption of Radiation Therapy

Interruption of planned radiation for 5 consecutive fractions or 10 fractions total due to AZD1775 (MK-1775)-attributable toxicity (and not due to technical issues).

Non-Hematological Dose-Limiting Toxicity

5.5.1.1 Any Grade 3 or Grade 4 non-hematological toxicity attributable to AZD1775 (MK-1775) with the specific exclusion of:

- Grade 3 nausea and vomiting of less < 3 days duration (Grade 3 nausea or vomiting \geq 3 days in the presence of antiemetics will be considered a DLT)
- Grade 3 liver enzyme elevation, including ALT/AST/GGT that returns to levels that meet initial eligibility criteria or baseline

THIS PROTOCOL IS FOR RESEARCH PURPOSES ONLY, SEE PAGE 1 FOR USAGE POLICY

within 7 days. See [Appendix X](#) for values that represent thresholds between CTCAE grades.

Note: For the purposes of this study the ULN for ALT is defined as 45 U/L.

- Grade 3 or 4 fever < 5 days duration.
- Grade 3 infection < 5 days duration.
- Grade 3 hypophosphatemia, hypokalemia, hypocalcemia or hypomagnesemia responsive to oral supplementation
- Any Grade 2 non-hematological toxicity attributable to AZD1775 (MK-1775) that persists for \geq 7 days and is considered sufficiently medically significant or sufficiently intolerable by patients that it requires interruption of AZD1775 (MK-1775) for 7 days.
- Note: Allergic reactions that necessitate discontinuation of study drug will not be considered a dose-limiting toxicity.

Hematological dose limiting toxicity

- Grade 3 thrombocytopenia (platelet count < 50,000/mm³)
- Grade 4 neutropenia

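### The final dose level can be declared the recommended dose on no DLTs in three to five patients, because the six-patient condition applies only to an MTD reached by de-escalation

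*Combined protocol and SAP*

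**What the plan says.** Section 11.3 uses a rolling-six design. Its text says that "if toxicity data is available for all three when the fourth participant entered and there are no DLTs, the dose is escalated". The table repeats this for four and five patients with no DLT and none pending. All of these rows carry the double-asterisk footnote: "If final dose level has been reached, the recommended dose has been reached".

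The single-asterisk footnote, on the de-escalation rows, reads: "If six patients already entered at next lower dose level, the MTD has been defined". A level is rejected as follows: "If two or more of a cohort of up to six patients experience DLT at a given dose level, then the MTD has been exceeded". Section 11.2 gives the target: "The MTD will be the maximum dose at which fewer than one-third of patients experience DLT".

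Section 11.1 plans for more patients than the footnote demands: "An additional 24 evaluable patients may be required to evaluate Dose Levels 5-7". That is six at each of three levels plus six for PK. The only stated minimum per level is two evaluable patients. The PK places are optional, open only after the dose is defined, are meant for patients under 12, and carry no DLT rule. The expansion to 12 in Section 11.2 applies only after two DLTs in six patients. Nothing in Section 11 requires the last level to be filled to six.

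**The concern.** At an intermediate level, escalating on 0/3 is provisional. If the next level proves too toxic, the trial comes back, and the lower level is called the MTD only with six patients entered there. At the final level there is no next level. The decision that would elsewhere mean carrying on becomes the answer to primary aim 1.1.1, on as few as three patients.

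Two things are at stake. One is the chance of accepting a final level whose true DLT rate is one-third or more. The other is how much evidence stands behind the recommended dose when it is reported, even if that dose is tolerable.

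**Working it through.** **1. The plan's own figures.** 3 levels × 6 + 6 for PK = 24 evaluable patients. For the ceiling, 3 × 12 + 6 = 42; 42 × 1.2 = 50.4, rounded up to 51; 26 + 51 = 77. These reproduce Section 11.1. The documents give no operating characteristics for the decision table and no limit on the chance of accepting a too-toxic level.

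**2. What each accepting result shows.** With 0 DLTs in n patients, the exact one-sided 95% upper limit for the DLT rate is 1 − 0.05^(1/n). For 1/6 it solves (1−p)^6 + 6p(1−p)^5 = 0.05.

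| Result | Upper limit |
|---|---|
| 0/3 | 63% |
| 0/4 | 53% |
| 0/5 | 45% |
| 0/6 | 39% |
| 1/6 | 58% |

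**3. Worst case.** Suppose all three patients always complete the window before a fourth enrols. The level is accepted on 0/3, or on 1/3 followed by 0 in the next three. With p the true DLT rate and q = 1 − p:

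- As written: q^3 + 3pq^2 × q^3.
- Six required, at most 1 DLT: q^6 + 6pq^5.
- At p = 1/3: 0.296 + 0.444 × 0.296 = 0.428, against 0.088 + 0.263 = 0.351.
- At p = 0.40: 0.216 + 0.432 × 0.216 = 0.309, against 0.047 + 0.187 = 0.233.
- At p = 0.50: 0.125 + 0.375 × 0.125 = 0.172, against 0.109.
- At p = 0.10: 0.729 + 0.243 × 0.729 = 0.906, against 0.886.

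**4. At the stated accrual.** Inputs from the documents: Section 11.1 "indicates that 1-2 patients per month are available", and Section 5.5 "The DLT observation period for the purposes of dose-escalation will be the entire duration of radiation therapy". The radiation course lasts 6 weeks, with missed fractions made up in week 7 or 8 (Section 5.1). Evaluability is judged within 8 weeks (Section 11.2). The window was therefore taken as 6 or 8 weeks. Assumptions not in the documents: Poisson arrivals, DLT times uniform over the window, no inevaluable patients. The Section 11.3 table was simulated with 100,000 runs per setting.

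| True DLT rate | Worst case | 1-2 per month | Six required | Excess, worst case | Excess, 1-2 per month |
|---|---|---|---|---|---|
| 1/3 | 42.8% | 35.4-37.5% | 35.1% | 7.7 | 0.3-2.4 |
| 40% | 30.9% | 23.8-25.8% | 23.3% | 7.6 | 0.5-2.5 |
| 50% | 17.2% | 11.2-12.8% | 10.9% | 6.3 | 0.3-1.9 |

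If accrual fell to 0.5 per month (an assumption, below the stated range), acceptance at 1/3 would be 38.6-39.5%.

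**5. Evidence behind a tolerable dose.** At a true rate of 10% and 1 patient per month, acceptances on 3, 4 or 5 patients were (18.3 + 12.5 + 8.3)/89.2 = 44% of all acceptances with a 6-week window, and (11.7 + 8.7 + 6.6)/88.9 = 30% with 8 weeks. At 2 per month the shares are (4.5 + 4.0 + 3.3)/88.7 = 13% and (1.9 + 1.6 + 1.5)/88.6 = 6%.

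**The case against.** The strongest reply is that the rolling six rarely stops at three. It does so only if all three patients have complete data when a fourth arrives, which is uncommon with a 6-8 week window and 1-2 patients a month. Section 2.6 supports this: Levels 1-4 enrolled 6, 6, 7 and 7 patients, although Levels 1-3 had no DLT. This stands, and it reduces the excess from 6-8 points to about 0-2.5.

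A reader who treated the design as a 3+3 might infer that most acceptances rest on 0/3 (at 40%, 21.6/30.9 = 70%). Under the actual rule and stated accrual, the share at true rates of 1/3 to 50% is about 2-25%.

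Six patients are also weak evidence. The upper limit after 1/6 is 58%, and even 0/6 does not exclude one-third. This stands too: the proposed rule removes an inconsistency but does not give precision.

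The footnotes also use different terms, MTD and recommended dose, and the one-third definition is written for the MTD. That is fair as a reading. But aim 1.1.1 offers the two as alternative answers to the same question, and Section 11.2 sets no separate toxicity standard for a recommended dose.

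Finally, Section 5.3 leaves room for levels above 7. The footnote then applies to whichever level is studied last, so the gap moves but does not close.

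**Conclusion.** The point holds as a gap in the decision rule with a small expected effect. The final level can be fixed as the recommended dose on 0/3, 0/4 or 0/5, while de-escalation requires six patients entered, and nothing afterwards revises it. The excess chance of accepting a level with a true DLT rate of 1/3 to 50% is at most about 6-8 points, and about 0-2.5 points at the stated accrual. The upper figures are exact binomial; the lower ones rest on the arrival and timing assumptions above. The larger practical effect is on a tolerable dose: at 1 patient per month and a 10% rate, about 30-45% of declared recommended doses would rest on fewer than six patients.

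Two stronger readings are not supported. A reader might infer that a too-toxic top level is accepted too often, but the documents set no acceptable probability, and the six-patient rule itself accepts a rate of one-third in 35% of trials. A reader might also set the top level against the adult figure of about 115 mg/m² in Section 2.6. That figure came from a combination with temozolomide as well as radiation, so it is not a direct comparator.

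**What to change.** Amend the double-asterisk footnote in Section 11.3 so that the final level studied becomes the recommended dose only once six DLT-evaluable patients there show at most one DLT. Fill the missing places from the six-per-level allowance already counted in the 24 evaluable patients of Section 11.1. Do not use the PK expansion for this: those places open only after the dose is defined and are meant for patients under 12. State separately that DLTs in the PK expansion count towards the final DLT rate reported at that dose.

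The cost is nothing when the cohort has already filled to six. Otherwise it is at most three more evaluable patients within the planned number. Accruing them takes 3/2 = 1.5 to 3/1 = 3 months, plus one further 6-8 week observation window. At a safe 10% DLT rate, acceptance falls from at most 90.6% to 88.6%. The accrual ceiling of 77 does not change.

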11.4 Inclusion of Children, Women and Minorities

The study is open to all participants regardless of gender or ethnicity. Review of accrual to past COG studies of new agents demonstrates the accrual of both genders and all NIH-identified ethnicities to such studies. Efforts will be made to extend the accrual to a representative population, but in a Phase 1 trial which will accrue a limited number of patients, a balance must be struck between patient safety considerations and limitations on the number of individuals exposed to potentially toxic or ineffective treatments on the one hand and the need to explore gender, racial, and ethnic aspects of clinical research on the other. If differences in outcome that correlate to gender, racial, or ethnic identity are noted, accrual may be expanded or additional studies may be performed to investigate those differences more fully.

11.5 Pharmacokinetic and Correlative Studies and Response Analysis

A descriptive analysis of pharmacokinetic (PK) parameters of AZD1775 (MK-1775) will be performed to define systemic exposure and other pharmacokinetic parameters. The PK parameters will be summarized with simple summary statistics, including means, medians, ranges, and standard deviations (if numbers and distribution permit).

Biologic activity of AZD1775 (MK-1775) will be explored using expression of p-CDC2, p-HH3 and γ -H2AX in PBMCs before and after administration of AZD1775 (MK-1775) using paired analysis methods.

While the primary aim of this study is to evaluate the toxicity of AZD1775 (MK-1775), patients will have disease evaluations performed as indicated in [Section 8.1](#). Disease response will be assessed according to criteria outlined in [Section 12.0](#), and will be reported descriptively. Progression-free survival and overall survival will also be summarized using the Kaplan-Meier method and including 95% confidence intervals. Both measurements of survival will be measured from the time of study entry.

All these analyses will be descriptive and exploratory and hypotheses generating in nature.

12.0 EVALUATION CRITERIA

12.1 Common Terminology Criteria for Adverse Events (CTCAE)

The descriptions and grading scales found in the revised NCI Common Terminology Criteria for Adverse Events (CTCAE) version 5.0 will be utilized for AE reporting. All

THIS PROTOCOL IS FOR RESEARCH PURPOSES ONLY, SEE PAGE 1 FOR USAGE POLICY

appropriate treatment areas should have access to a copy of the CTCAE version 5.0. A copy of the CTCAE version 5.0 can be downloaded from the CTEP website (http://ctep.cancer.gov/protocolDevelopment/electronic_applications/ctc.htm).

